### 5.2.3 Mean pain relief for Weeks 1-4, Weeks 5-8, and 3, 6, 9, and 12 months after SOT

The analysis of treatment effect on average pain compares the mean percent improvement from baseline to the specified intervals after start of therapy. The mean percent improvement in Group #1 for Weeks 1-4, Weeks 5-8, and 3 months will be compared to Group #2 for Weeks 1-4, Weeks 5-8, and 3 months, respectively. The mean percent improvement in Group #1 at 6, 9, and 12 months will be compared to Group #2 at 3 months (the longest follow-up before crossover). A two-sided Wilcoxon rank-sum test will be performed to assess the difference between groups.

During the home trial (*i.e.*, Weeks 1-4 or Weeks 5-8 of the home trial), the average pain intensity scores will be determined for each subject by taking the mean of the daily average (BPI-SF Question #5) reported in the 7-day diary at baseline compared to the mean score for in the 7-day diaries during Weeks 1-4 or Weeks 5-8 of the home trial, respectively

Similarly, at 3, 6, 9, or 12 months after start of therapy, the mean
verage pain intensity scores will be determined by taking the mean of the daily average pain (BPI-
F Question #5) reported in the 7-day diary at baseline compared to the mean pain score in the 7-
ay diaries preceding each visit
. The null hypothesis is that the distribution of mean change in
verage scores is the same for the two groups; the alternative hypothesis is that one of the
istributions is shifted relative to the other distribution by a constant amount. Testing will be
onducted at the 0.05 level of significance.

# 5.2.4 Pain Medication Usage at 4 weeks, 8 weeks, and 3, 6, 9, and 12 months after SOT 1) Pain medication usage between groups

The analysis of pain medication usage examines changes in medication usage between the two groups. Changes in medication will be reviewed for Weeks 1-4 of therapy, Weeks 5-8 of therapy, and at 3, 6, and 12 months after the start of therapy. For this analysis, a blinded third-party medication committee will review medications of study participants collected for each diary collection period and will use the following convention for scoring medication changes, in comparison to the baseline diary medications:

- No change = No change in dosage or change is not clinically meaningful to impact pain outcomes.
- Increase = Clinically meaningful increase in medication that would impact pain outcomes.
- **Decrease** = Clinically meaningful decrease in medication that would impact pain outcomes.

The blinded third-party medication committee (comprised of three clinicians experienced in the treatment and management of pain) will serve as the evaluator for all clinical sites. Final determinations of changes in medication usage will require agreement among at least two of the three blinded evaluators. In cases where there is 1:1:1 tie, the medication review committee will convene to discuss and adjudicate the final determination.

The distribution of changes in opioid pain medication usage (decrease/no change/increase) will be reported first using an exact Mantel-Haenszel test to compare the ordered distributional responses (percentage of subjects within each category) between Group #1 and Group #2. Group #1 at Weeks 1-4, Weeks 5-8, and 3 months will be compared to Group #2 at Weeks 1-4, Weeks 5-8, and 3 months, respectively. Group #1 at 6, 9, and 12 months will be compared to Group #2 at 3 months (the longest follow-up before crossover). Assuming there is a statistically significant difference in the ordered distributional responses between Group #1 and Group #2 at a given timepoint, a subsequent statistical test will be carried out to compare between groups the percent of subjects categorized as having a decrease in opioid pain medication. In addition to opioids, this analysis will also be repeated for analysis of all pain medications, and non-opioid analgesic usage independently.

The null hypothesis is that the difference in the proportion of subjects categorized as "decrease in pain medication" between the treatment and control groups is not statistically significant. The alternative hypothesis is that the difference in the proportion of subjects categorized as "decrease in pain medication" is statistically significant at the 0.05 significance level.

Page 8 of 19

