### 4.2.1.3 Exclusion Criteria

- 1. Change of prescribed medications affecting knee pain within the past 4 weeks
- 2. Current high opioid use (i.e., mg oral MED in a single day)
- 3. If subject reports any opioid use within the past 4 weeks subject must not have used opioids daily for the month preceding knee replacement
- 4. If subject reports any opioid use within the past 4 weeks subject must not have used mg oral

	MED on any day during the month preceding knee replacement
5	Body Mass Index (BMI) > 40 kg/m 
	Compromised immune system based on medical history
0.	
	or other conditions that places the subject at increased risk in the opinion of the investigator
7.	History of valvular heart disease
	Deep brain stimulation (DBS), an implanted active cardiac implant, or
	any other implantable neurostimulator whose stimulus current pathway
	may overlap the SPRINT Stimulator's current pathway.
9.	History of bleeding disorder (e.g., hemophilia) or subjects with active
	anticoagulation whose use or temporary modification for the lead
	placement procedure places the subject at increased risk in the
40	opinion of the investigator.
10	Confounding conditions
11	Diagnosis of Diabetes Mellitus Types I or II
	History of nerve damage in the affected leg
12	Thistory of herve damage in the unested log
13	Confirmed tape or adhesive allergy
	Contraindications to the proposed anesthetic protocol
15	Any other condition that may interfere with ability to participate in a
	clinical trial
	as determined by the
	Investigator
16	Prisoners, minors, or individuals that report to investigators (e.g.,
4-	students, employees)
	History of substance abuse
18	Potential secondary gain issues related to knee pain (e.g., pending
10	claims or receiving disability)  Botulinum toxin injection in the affected in the affected
19	limb
20	Steroid injection
21.	Subject has participated in any drug or device trial in the past 30 days. Subject has participated in previous SPR Therapeutic sponsored study
	Changaraa ciilay

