### 5.0 Endpoint Analyses

Analyses of the primary and secondary effectiveness endpoints will be conducted on the full analysis set and the per-protocol population set at each specified study interval. The full analysis

set is considered the primary population for formal statistical hypothesis testing.
5.1 Primary Endpoint  Relief of postoperative pain will be evaluated using the average pain intensity. All subject will record pain scores daily for the qualifying knee (i.e., with total knee implant and qualifyin pain) in the 7-day diaries using BPI-SF Question #5. Data will be collected  Each subject must have ≥50% reduction is
pain relative to baseline to be considered a success in the primary efficacy endpoint analysis. Missing data will be handled according to Section 8.2. The primare endpoint analysis will be based upon the Full Analysis Set, including imputation for missing data due to missed visits and early termination. An analysis will also be performed based on the Perotocol population,
Group #1 will receive active stimulation and Group #2 wi receive sham stimulation during the 8-week home trial.
The primary endpoint compares the proportion of subjects in Group #1 relative to that in Group #2 that achieve $\geq 50\%$ reduction in pain from baseline to Weeks 5-8 of the home trial using Fisher's exact test. The null hypothesis (H 0 ) is that the PNS treatment (Group #1, activational stimulation) is equal to the control (Group #2, sham stimulation) in providing pain relief. The alternative hypothesis (H a ) is that Group #1 has a proportion of successes that is not equal to the

 $H_0$ : proportion of successes in Group #1 = proportion of successes in Group #2  $H_a$ : proportion of successes in Group #2  $\neq$  proportion of successes in Group #2

If the proportion of successes in the PNS treatment is larger than the proportion of successes in the control during the Weeks 5-8 of the home trial and statistically significantly different (p < 0.05, two-sided), then the null hypothesis is rejected at the 0.05 level of significance, which will indicate that the therapeutic effect is clinically significant and superior to the placebo effect[2].

proportion of successes in Group #2.

treatment effect for time from TKR.

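### The opioid-decrease comparison is made over all subjects, including those with no baseline use who cannot decrease; a baseline-user comparison and stratification would make it sharper and easier to read

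*SAP*

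**What the plan says.** SAP 5.2.4(1) has a blinded three-clinician committee classify each subject, per diary period, as decrease, no change or increase, "in comparison to the baseline diary medications". No change is defined as "No change in dosage or change is not clinically meaningful to impact pain outcomes".

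An exact Mantel-Haenszel test is then used to "compare the ordered distributional responses (percentage of subjects within each category) between Group #1 and Group #2". A second test follows conditionally: "Assuming there is a statistically significant difference in the ordered distributional responses between Group #1 and Group #2 at a given timepoint", the groups are compared on "the percent of subjects categorized as having a decrease in opioid pain medication". The sequence is repeated for all pain medications and for non-opioid analgesics. The section words its null and alternative hypotheses in terms of the proportion with a decrease.

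On the population, SAP 5.0 states: "Analyses of the primary and secondary effectiveness endpoints will be conducted on the full analysis set and the per-protocol population set". The visible definitions of those sets (SAP 6.2 and 6.3) do not mention medication use.

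On entry, Protocol 4.2.1.3 treats opioid use as conditional: "If subject reports any opioid use within the past 4 weeks subject must not have used opioids daily for the month preceding knee replacement". It also excludes high current use (threshold not visible). Nothing in the visible criteria requires opioid use.

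SAP 3.1 randomizes primary TKR separately from PKR and revision TKR; no medication stratum is visible. SAP 4.0 makes all secondary hypotheses exploratory, tested at two-sided 0.05 without multiplicity adjustment.

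**The concern.** A subject who takes no opioid at baseline can only be scored no change or increase. Counting such subjects in the percent-decrease comparison adds structural zeros to both arms. This has three consequences:

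- The percentage cannot exceed the share of baseline users, so a large effect among users looks small.
- The between-arm difference moves with the number of users each arm happened to enrol.
- Power is lower than in a comparison among users.

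The same applies to the non-opioid and all-analgesic repeats, for any subject with no baseline use of that class.

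Protocol 11.4 cites reduced opioid use among the potential benefits that justify the risk, so a readable opioid result matters even though the endpoint is secondary.

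**Working it through.** The visible documents give no sample size, opioid prevalence or power for this analysis, so there is no planned figure to reproduce. What follows is an illustration.

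**Inputs**
- u, share using opioids at baseline: not given. Protocol 2.2 cites 25-40% still using opioids 90 days after TKR. I use that as a range; time from surgery in this trial is not visible.
- n per arm: not visible; 25, 40 and 60 assumed.
- Decrease among users: 60% v 30%, assumed.
- Follow-up test: not named in the SAP; two-sided Fisher exact test assumed, ignoring the gate.

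**1. Dilution.** A non-user contributes zero decreases, so the all-subject rate is u × (rate among users) and the difference is u × (60 − 30) points.
- u = 25%: 15% v 7.5%, difference 7.5 points
- u = 30%: 18% v 9%, difference 9 points
- u = 40%: 24% v 12%, difference 12 points

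**2. Power of the decrease comparison.** All subjects by exact enumeration; users only by simulation (20,000 runs, number of users random in each arm).

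| n per arm | u | All subjects | Baseline users |
|---|---|---|---|
| 25 | 25% | 5% | 10% |
| 25 | 40% | 11% | 18% |
| 40 | 25% | 10% | 18% |
| 40 | 30% | 14% | 23% |
| 40 | 40% | 21% | 32% |
| 60 | 25% | 17% | 29% |
| 60 | 40% | 31% | 50% |

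**3. Size for 80% power.** Normal approximation: n = [1.96√(2p̄(1−p̄)) + 0.842√(p₁(1−p₁) + p₂(1−p₂))]² / (p₁−p₂)², with p̄ the mean of the two rates.
- Among users, 60% v 30% needs 42 users per arm, which means 42/u randomized per arm: 168 at u = 25%, 105 at u = 40%.
- Over all subjects: 15% v 7.5% needs 278 per arm; 24% v 12% needs 160.

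**4. Chance imbalance in baseline use.** The SD of the between-arm difference in user share is √(2u(1−u)/n). At u = 30% and n = 40 this is √(2 × 0.3 × 0.7/40) = 10.2 points. Under simple randomization with u = 25-40%, the chance of a gap of 15 points or more is 25-31% at 25 per arm, 16-21% at 40 and 7-11% at 60.

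Suppose there is no treatment effect, 45% of users decrease in both arms, and the arms hold 50% v 30% users. The expected all-subject rates are 0.50 × 45 = 22.5% and 0.30 × 45 = 13.5%, a 9-point gap that is not due to treatment. At 40 per arm (20 v 12 users) the Fisher test then rejects 7.8% of the time, against 0.8% with 16 v 16.

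**5. Validity.** Averaged over randomization, with 45% of users decreasing in both arms and u = 25-40%, the all-subject Fisher test rejects 1.2-2.8% of the time. That is below 5%.

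**6. Stratifying the ordinal test.** A separate set of assumptions was used here: 30% users; among users, decrease 60% v 25% and increase 10% v 20%; among non-users, increase 3% v 5%; asymptotic mean-score test in place of the exact one. Stratifying by baseline use raises power from about 32% to 35% at 40 per arm and from about 45% to 49% at 60 per arm.

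**The case against.** The strongest case against is that nothing here is an error. The share of all treated subjects who reduce opioids is a legitimate quantity; the share among users answers a different question. Since non-users are structurally zero, the user percentages can be recovered by dividing by the user share (18%/30% = 60%) once the number of users per arm is reported. The ordinal test gains only a few power points from stratification, and a users-only comparison rests on few subjects. This largely stands, and it sets the weight of the point. It does not remove the power difference in step 2, and the visible plan does not call for the user counts that the division needs.

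A reader might also infer stronger things that the documents do not support:

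- **That the plan ignores baseline use.** Every score is made against the baseline diary. What is missing is a restriction or stratum in the group comparison.
- **That the result is biased or the type I error inflated.** Chance imbalance is not systematic bias. The 7.8% in step 4 is conditional on one chosen split.
- **That non-users are only noise.** They can start opioids, and the ordinal test picks that up.
- **That the decrease result is withheld unless the ordinal test is significant.** The category percentages are reported first in any case. Only the subsequent test depends on the condition "Assuming there is a statistically significant difference in the ordered distributional responses". Such a gate is compatible with SAP 4.0, which permits tests at 0.05 without claims of significance.
- **That many subjects have no opioid use.** Excluding high use does not show this; prevalence is not given.

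Finally, the content of SAP 5.2.10, most of section 8 and section 8.2 is not visible, so a baseline-user analysis there cannot be excluded. SAP 5.2.4 does not refer to one.

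**Conclusion.** The point holds as an improvement to a secondary analysis. As visible, SAP 5.2.4(1) compares percent decrease over all subjects without restricting to, or stratifying by, baseline use of the class, although non-users are eligible and cannot decrease. The percentage is therefore capped by prevalence, partly reflects the number of users enrolled in each arm, and has less power than a comparison among users.

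On the assumed inputs, a 30-point difference among users appears as 7.5 to 12 points overall. Power for the decrease comparison is about 5 to 18 percentage points lower over all subjects across the settings tabulated. Stratifying the ordinal test is worth about 2-4 points. These sizes rest on the assumed prevalence, effect, sample size and follow-up test. The structural zero does not.

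The 9 and 30 points are two estimands, not a wrong and a right answer. The planned test is valid, the endpoint is exploratory, and the primary conclusion is unaffected.

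**What to change.** Amend SAP 5.2.4(1) before any unblinded analysis:

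1. Stratify the exact Mantel-Haenszel test by baseline use (yes/no) of the medication class being analysed.
2. State how a subject with no baseline use is scored, and report the number of baseline users per arm for each class.
3. Compare percent decrease among baseline users, with a confidence interval, at each concurrent timepoint (Weeks 1-4, Weeks 5-8, 3 months), whether or not the ordinal test is significant. Name the test.
4. Keep the all-subject category percentages, and report new use among baseline non-users separately.

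Baseline use is recorded before randomization, so the comparison among users remains randomized. No new data are needed, because the baseline diary already captures medication.

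The cost is SAP wording and wide intervals. With 40 per arm and 30% users (both assumed) there are about 12 users per arm. At 60% v 30% the standard error is √(0.24/12 + 0.21/12) = 0.194, so a 95% interval is roughly ±38 points. That imprecision should be shown alongside the estimate.

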### 2) Effect of pain medication on reductions in postoperative pain

The effect of change in medication will also be examined using logistic regression with patient outcome at the primary endpoint (success/failure) as the dependent variable and two binary independent variables, one which indicates treatment, and the other which serves as a potential explanatory (independent) variable for change in medication defined as follows: increase in overall medication use versus no change/decrease. Changes in medication will be reviewed for Weeks 1-4 of therapy, Weeks 5-8 of therapy, and at 3 months after the start of therapy in Group #1 and Group #2, and at 6, 9, and 12 months after the start of therapy in Group #1. The purpose of the analysis is to determine whether changes in medication are a statistically significant predictor of success above and beyond the therapeutic effect (*i.e.* evaluated as a covariate) and will not affect the results of the primary endpoint. A blinded third-party medication committee will review medications of study participants collected for each diary collection period and will use the following convention for scoring medication changes, in comparison to the baseline diary medications:

- **No change** = No change in dosage or change is not clinically meaningful to impact pain outcomes.
- Increase = Clinically meaningful increase in medication that would impact pain outcomes.
- **Decrease** = Clinically meaningful decrease in medication that would impact pain outcomes.

The blinded third-party medication committee (three clinicians experienced in the treatment and management of pain) will serve all clinical sites. Final determinations require agreement among at least two of the three blinded medication evaluators. In cases where there is a 1:1:1 tie, the medication review committee will convene to discuss and adjudicate the final determination.

This analysis will be conducted for opioids, then repeated for analysis of all pain medications, and then non-opioid analgesic usage independently.

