### 4.1 Primary Hypothesis

Overall Proportion of Success in Group #1 (G1) with active PNS vs. Group #2 (G2) with sham PNS for reduction of postoperative pain following a primary total knee replacement orthopedic surgery. The null  $(H_0)$  and alternative hypotheses  $(H_a)$  are:

H0: 
$$p_{G1} - p_{G2} = 0$$
 vs.

Ha: 
$$p_{G1} - p_{G2} \neq 0$$

where p G1 and p G2 are the proportions of success in average pain intensity during Weeks 5-8 in active PNS Group #1 and sham PNS Group #2, respectively.

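### Does the medication regression in SAP 5.2.4(2) have to be rewritten because it does not name the medication period that enters the model?

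*SAP*

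**What the plan says.** The dependent variable is primary-endpoint success. SAP 4.1 ties that to Weeks 5-8, since the primary hypothesis concerns "the proportions of success in average pain intensity during Weeks 5-8 in active PNS Group #1 and sham PNS Group #2". In SAP 5.2.4(2) the model is fitted "with patient outcome at the primary endpoint (success/failure) as the dependent variable and two binary independent variables, one which indicates treatment". The second variable separates subjects whose overall medication use rose from those whose use fell or did not change; its definition gives no period.

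The next sentence says that medication changes will be reviewed at Weeks 1-4, Weeks 5-8 and 3 months in both groups, "and at 6, 9, and 12 months after the start of therapy in Group #1". The stated purpose is to "determine whether changes in medication are a statistically significant predictor of success above and beyond the therapeutic effect", and the same sentence adds that the analysis "will not affect the results of the primary endpoint". Scoring is then described: "A blinded third-party medication committee will review medications of study participants collected for each diary collection period". The section closes by repeating the analysis for opioids, all pain medications and non-opioid analgesics.

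SAP 4.0 treats all secondary hypotheses as exploratory and rules out claims of significance from them. It also refers to Section 8.0 for analysis methods. Most of Section 8 and the content of Section 5.2.10 are not visible in the public text.

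**The concern.** Read quickly, the list of review periods looks like a list of models, one per period, each regressing Weeks 5-8 success on treatment and on medication change in that period. Two faults would follow.

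First, time order. A score taken at 3 months or later is measured after success or failure has been settled. Subjects whose pain did not improve may then take more medication, and the regression would report that consequence as a predictor of success.

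Second, identifiability. At 6, 9 and 12 months the list names Group #1 only. With one group the treatment indicator is constant, so medication cannot be tested over and above the treatment effect.

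At stake would be a misleading secondary statement that medication change explains, or fails to explain, the pain result.

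**Working it through.** The plan gives no figure for this analysis, so there is none to reproduce. The check compares timing, design and wording.

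**Timing.** The outcome period ends at Week 8. Taking 3, 6, 9 and 12 months as 13, 26, 39 and 52 weeks:

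| Review period | Groups listed | Weeks after Week 8 | Treatment term estimable |
|---|---|---|---|
| Weeks 1-4 | both | none (before the outcome period) | yes |
| Weeks 5-8 | both | none (concurrent) | yes |
| 3 months | both | 13 - 8 = 5 | yes |
| 6 months | Group #1 | 26 - 8 = 18 | no |
| 9 months | Group #1 | 39 - 8 = 31 | no |
| 12 months | Group #1 | 52 - 8 = 44 | no |

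Four of the six periods fall after the outcome period, and three are in Group #1 only. Two are not late and exist in both groups.

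**Design.** The model has three columns: intercept, treatment, medication increase. With both groups the rank is 3 of 3. With Group #1 only, the treatment column equals the intercept column and the rank is 2 of 3. A model with medication alone could still be fitted, but it would not be the one the SAP describes. Pairing later Group #1 data with Group #2 at 3 months, as SAP 5.2.4(1) does, restores rank 3 of 3. However, adding a column for time of measurement gives rank 3 of 4, so treatment and timing cannot be separated.

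**Wording.** Three features bear on whether the later periods were meant to enter the model.

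1. Part (1) of the same section opens with a parallel sentence: "Changes in medication will be reviewed for Weeks 1-4 of therapy, Weeks 5-8 of therapy, and at 3, 6, and 12 months". A later paragraph there states which periods are compared, and it includes 9 months, which the review sentence omits. In part (1), then, the review sentence does not define the analysis. Part (2) has a review sentence of the same kind and no paragraph assigning periods to models.
2. Part (2) says when the model is repeated: by drug class. One period gives 3 × 1 = 3 models; all six would give 3 × 6 = 18. The text mentions only the three-fold repetition and speaks of the analysis in the singular.
3. The stated aim needs a treatment term. A reading under which half the models (3 of 6 periods) cannot meet that aim is the less likely one.

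The split of the list by group has a plain explanation. Under the protocol, Group #2 either leaves or may cross over after the 3-month visit, so a scoring schedule would look the same.

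**Simulated size.** One can assume that medication has no effect on success, that success is 60% versus 30%, and that a later increase occurs in 10% of successes and 20% to 40% of failures. With 25 to 60 per group, a likelihood-ratio test in a 3-month model then flags medication in 18% to 96% of simulated trials, against about 5% to 7% when later medication is unrelated to success. None of these inputs is in the documents, and the sample size is not visible. The result shows that an association built into the simulation can be detected. It does not measure a problem in this trial.

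**The case for a change.** The best case for a change is that the list stands between the model and its purpose, assigns periods by group, and is separate from the sentence on committee scoring. That makes it readable as a list of covariate periods. Even as a scoring schedule, it leaves open whether the Weeks 1-4 or the Weeks 5-8 score is used, so two analysts could fit different models. Exploratory status does not settle what the coefficient means.

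Part of this stands. The visible text does not name the period, and the choice between the two early periods is open. The time-order point would also be sound if later scores were used. It needs one qualification: scores are changes from baseline, so an increase recorded at 3 months may have begun during treatment, and late measurement alone does not prove that medication had no bearing on the outcome. The identifiability point is sound for 6 to 12 months but does not exclude the 3-month score, which exists in both groups; only timing argues against that one.

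What does not stand is the step from an unnamed period to a faulty analysis. It requires a reading that the text does not state and that works against the model's own purpose. A rule on periods could also sit in the parts of Sections 5.2.10 and 8 that are not visible.

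**Conclusion.** The concern identifies missing detail, not an error. A competent analyst asked to relate Weeks 5-8 success to treatment and medication change would use a score from Weeks 1-4 or Weeks 5-8, in both groups. The 3- to 12-month scores would be kept for the between-group comparisons in SAP 5.2.4(1). Either early choice gives an estimable model. Both are measured after randomization, and the Weeks 5-8 score is concurrent with the outcome, so the result is an association whichever is used.

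The consequence is small. The regression is not among the nine secondary hypotheses in SAP 4.2, where the medication item concerns usage between groups. It falls under the exploratory status in SAP 4.0, and the SAP says it leaves the primary result unaffected. Rewriting the section would not alter the primary test, the data collected or any decision.

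This rests on two assumptions: that the review list is the scoring schedule or is read sensibly by the analyst, and that the sections not visible do not direct the later scores into this model.
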